5.3.5.2 Clinical Protocol

Table 10: Allowable TRC105 Dose Modifications

Toxicity Attributed to TRC105	Dose Adjustment for Next Dose of TRC105	
	10 mg/kg weekly	15 mg/kg every 2 weeks
Grade 1 or 2	Maintain Dose Level	Maintain Dose Level
Grade 3 or 4		
• 1 st appearance	8 mg/kg weekly	12 mg/kg every 2 weeks
• 2 nd appearance	6 mg/kg weekly	10 mg/kg every 2 weeks
• 3 rd appearance	4 mg/kg weekly	8 mg/kg every 2 weeks
• 4 th appearance	Discontinue TRC105 treatment permanently	Discontinue TRC105 treatment permanently*
*After discussion with and agreement of the Sponsor, patients receiving TRC105 every two weeks have the option to return to weekly dosing at the lowest level (i.e., 4 mg/kg weekly), if 8 mg/kg every 2 weeks is not tolerable (i.e., 4 th appearance of a Grade 3 or 4 toxicity attributable to TRC105 occurs) and the investigator believes that the patient is receiving benefit from the treatment.		

Patients with arterial thrombosis or grade 3 or 4 venous thrombosis should be removed from study. Patients with grade 1 or 2 venous thrombosis who require anticoagulation will have their TRC105 therapy interrupted. TRC105 therapy may resume once the following criteria are met:

- The patient is on a stable dose of heparin or low molecular weight heparin.
- The patient has a platelet count > 100,000.
- The patient has not had a hemorrhagic event of grade 2 or higher while on study.
- The patient does not have a pathological condition that carries a high risk of bleeding (e.g., tumor involving major vessels).
- The patient is benefiting from TRC105 therapy (no evidence of disease progression).

TRC105 and pazopanib should be held for two weeks prior and for two weeks following surgical procedures. However, resumption of study treatment can be shorter (but no less than 7 days) or longer than two weeks based on clinical judgement of adequate wound healing and recovery from the procedure. For **minor procedures** (e.g., port placement), TRC105 (and pazopanib) should be held for at least 1 week prior and for at least 1 week after (or until adequate healing).

TRC105 DOSING DELAY: If a patient misses a scheduled weekly TRC105 dose and dosing is resumed \geq 10 days after the last dose or if a patient misses a scheduled every 2 week dose and dosing is resumed \geq 17 days after the last dose, premedication (including methylprednisolone) and TRC105 are to be administered as described in [Table 11](#). **Split dosing is not required.** However, it is recommended that if the patient experienced a severe headache with a previous

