6.1.7. TRC105 Dose Modification/Dose Delays

In cycle 3 and beyond (and beginning in cycle 2 of the phase 2 portion), TRC105 dose reductions are allowed for grade 3 or 4 related adverse events that resolve to grade 1 or baseline (including anemia). Treatment dose delays cannot exceed 8 consecutive weeks (i.e., both TRC105 and pazopanib dosing held). However, patients who cannot tolerate pazopanib or TRC105 therapy and who demonstrate a response of complete response (CR), partial response (PR) or stable disease (SD) with the combination and are thought to benefit from continued single agent therapy may continue on study on TRC105 or pazopanib alone per Section 5.3 of the protocol.

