5.3.5.2 Clinical Protocol

infusion, the first TRC105 dose upon resumption should be administered over two days as was done for the initial dose, see [Table 12](#).

Table 11: TRC105 dosing after Dose Delay (with no split dosing)

	CxDy	CxDy	CxDy	CxDy	CxDy+
TRC105 Dose (mg/kg)	10 or 15	10 or 15	10 or 15	10 or 15	10 or 15
Infusion Duration (hours)	4	2	1	1	1
Premedication					
Methylprednisolone (mg)	100	0	0	0	0
Famotidine (mg)	20	20	20	20	0
Cetirizine (mg)	10	10	10	10	0
Acetaminophen (mg)	650	650	650	650	650

Note that acetaminophen should NOT be discontinued.

Table 12: TRC105 Dosing after Dose Delay (with split dosing)

	Day 1 resuming TRC105	3 days later	Weekly or every 2 weeks from Day 1	Weekly or every 2 weeks	CxDy+
TRC105 Dose (mg/kg)	3	7 or 12	10 or 15	10 or 15	10 or 15
Infusion Duration (hours)	4	2	1	1	1
Premedication					
Methylprednisolone (mg)	100	100	0	0	0
Famotidine (mg)	20	20	20	20	0
Cetirizine (mg)	10	10	10	10	0
Acetaminophen (mg)	650	650	650	650	650

Note that acetaminophen should NOT be discontinued.

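### The restart tables after a TRC105 dose delay print only full doses, so a patient already dose-reduced and then delayed for another reason has no correct printed restart dose

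*Combined protocol and SAP*

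**What the plan says.** Section 6.1.7 covers both dose reductions and dose delays.

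- **Reductions.** From cycle 3, or from cycle 2 in phase 2, "TRC105 dose reductions are allowed for grade 3 or 4 related adverse events that resolve to grade 1 or baseline". Table 10, under the column heading "Dose Adjustment for Next Dose of TRC105", gives three steps: 8, 6 and 4 mg/kg weekly, or 12, 10 and 8 mg/kg every two weeks. A fourth event means permanent discontinuation. Under the footnote, every-two-week patients who cannot tolerate 8 mg/kg "have the option to return to weekly dosing at the lowest level (i.e., 4 mg/kg weekly"), with the sponsor's agreement.
- **Delays.** When dosing resumes at least 10 days after the last weekly dose, or at least 17 days after the last every-two-week dose, "premedication (including methylprednisolone) and TRC105 are to be administered as described in" Table 11. Splitting is not required. After an earlier severe headache, however, the section recommends that the first dose on resumption "should be administered over two days as was done for the initial dose", as in Table 12.
- **The printed doses.** Table 11 shows 10 or 15 mg/kg in all five columns, the last of which is open-ended. Table 12 shows 3, then 7 or 12, then 10 or 15 mg/kg. The only note under either table concerns acetaminophen.
- **Interruptions for other reasons.** "Patients with grade 1 or 2 venous thrombosis who require anticoagulation will have their TRC105 therapy interrupted". The section also recommends holds around surgery and minor procedures.

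**The concern.** The restart instruction covers TRC105 itself as well as premedication and infusion time. It also applies at a stage of treatment when reductions are already permitted. Yet the dose rows it points to contain only the two full doses, and nothing makes them subject to Table 10.

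The exposed patient is one who was reduced for toxicity and is later held for something else. A site that follows Table 11 as printed would put that patient back on the full dose and, because the last column is open-ended, keep the patient there. Section 2.5.1 names TRC105 dose reduction among the responses to anemia, so such a restart would undo a protective step. What is at stake is the safety of individual patients. The trial's inference is not involved.

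**Working it through.** The plan gives no figure to reproduce. The check sets Tables 10, 11 and 12 side by side.

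**Which doses the restart tables print.** In Table 12, 3 + 7 = 10 and 3 + 12 = 15. The printed figures are therefore the full weekly dose and the full every-two-week dose.

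**Printed restart dose against the Table 10 dose (mg/kg).**

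| Schedule | Table 10 level | Printed restart | Ratio | Balance after 3 | Printed second portion |
|---|---|---|---|---|---|
| Weekly | 8 | 10 | 10/8 = 1.25 | 8 − 3 = 5 | 7 |
| Weekly | 6 | 10 | 10/6 = 1.67 | 6 − 3 = 3 | 7 |
| Weekly | 4 | 10 | 10/4 = 2.5 | 4 − 3 = 1 | 7 |
| Every 2 weeks | 12 | 15 | 15/12 = 1.25 | 12 − 3 = 9 | 12 |
| Every 2 weeks | 10 | 15 | 15/10 = 1.5 | 10 − 3 = 7 | 12 |
| Every 2 weeks | 8 | 15 | 15/8 = 1.875 | 8 − 3 = 5 | 12 |

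**Coverage.** Of the six reduced levels, five (8, 6 and 4 weekly; 12 and 8 every two weeks) do not appear in Table 11's dose row. The sixth, 10 mg/kg every two weeks, appears only because it equals the full weekly dose.

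**Whether a delay for another reason can reach the triggers.** These are the holds in Section 6.1.7, if followed as recommended:

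- Surgery: 14 + 14 = 28 days, or 14 + 7 = 21 days with the shortest allowed resumption. Both exceed 10 and 17 days.
- Minor procedure: at least 7 + 7 = 14 days. This exceeds 10 days but does not necessarily reach 17.

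The holds are recommendations, and an unplanned procedure cannot have the hold beforehand. Withdrawal criterion 2 in Section 5.3 may also remove some patients who need surgery. For thrombosis, Section 6.1.7 sets conditions for resuming but no fixed duration, so the gap cannot be calculated.

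**Whether other text fills the gap.** No sentence says that a reduced patient restarts at the reduced level. Several provisions point that way, and they are weighed under the objection.

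**The case against.** The strongest reply is that the figures are labels for the two regimens, and that the rest of the protocol shows no re-escalation is meant. Most of this stands as evidence of intent.

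- Table 10 only goes down, counts events cumulatively and ends in discontinuation. Its footnote keeps a patient who changes schedule at the lowest level.
- Where the protocol wants doses to go back up, it says so. Section 6.2.6 provides for pazopanib increases as well as decreases, in 200 mg steps. TRC105 has no equivalent.
- Full doses are printed without exception elsewhere, in Section 6.1.2.2 and in footnote 11 to Table 6. Nobody would read those as cancelling Table 10.
- The Table 12 split is to follow the initial dose, which Section 6.1.6 defines as 3 mg/kg and then the balance. That largely settles the second portion once the total dose is known.
- The entry 10 or 15 already requires the reader to apply the patient's own schedule. What changes across Table 11 is infusion time and premedication.

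A reader might infer that Tables 10 and 11 conflict outright when the delay was caused by a new grade 3 or 4 TRC105-related event. The documents do not support that. The first dose on resumption is the next dose, Table 10 is the rule specific to toxicity, and it should be read as governing, although the tables do not say so.

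What the reply leaves is the patient reduced earlier and then held for an unrelated reason. For that patient the Table 10 heading, tied to the next dose after an event, does not expressly cover the restart, whereas Section 6.1.7 points directly to Table 11. The correct dose must be inferred against a dosing instruction.

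**Conclusion.** The point holds as a minor dosing-safety defect. Followed as printed, the restart rule gives an already reduced patient, delayed for another reason, 1.25 to 2.5 times the reduced dose on the weekly schedule. On the every-two-week schedule the range is 1.25 to 1.875 times. These ratios assume a literal reading and, for the every-two-week schedule, that 15 is the figure applied.

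Two stronger readings should be avoided. A reader might infer that the protocol intends a return to full dose after any delay, but the reduction-only ladder and the absence of any written TRC105 re-escalation argue strongly against that. A reader might also take the ratios as the exposure to expect in the trial. They measure the consequence of one misreading. The documents do not show how often a reduced patient would have a qualifying delay, or how sites would read the tables, and no effect on any endpoint can be derived.

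**What to change.** - In Tables 11 and 12, replace the entry 10 or 15 with *current assigned dose after any Table 10 reduction*. Adding that this includes a reduction triggered by the event that caused the delay would also make Table 10's precedence explicit.
- In Table 12, replace 7 or 12 with *balance of the current assigned dose*. For example, a patient at 4 mg/kg weekly would receive 3 and then 1 mg/kg.
- In Section 6.1.7, add one sentence: *A dose delay does not reverse an earlier TRC105 dose reduction.*

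The cost is an edit to the dose rows of two tables and one added sentence. Sample size and analysis are unaffected.

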5.3.5.2 Clinical Protocol

infusion, the first TRC105 dose upon resumption should be administered over two days as was done for the initial dose, see [Table 12](#).

Table 11: TRC105 dosing after Dose Delay (with no split dosing)

	CxDy	CxDy	CxDy	CxDy	CxDy+
TRC105 Dose (mg/kg)	10 or 15	10 or 15	10 or 15	10 or 15	10 or 15
Infusion Duration (hours)	4	2	1	1	1
Premedication					
Methylprednisolone (mg)	100	0	0	0	0
Famotidine (mg)	20	20	20	20	0
Cetirizine (mg)	10	10	10	10	0
Acetaminophen (mg)	650	650	650	650	650

Note that acetaminophen should NOT be discontinued.

Table 12: TRC105 Dosing after Dose Delay (with split dosing)

	Day 1 resuming TRC105	3 days later	Weekly or every 2 weeks from Day 1	Weekly or every 2 weeks	CxDy+
TRC105 Dose (mg/kg)	3	7 or 12	10 or 15	10 or 15	10 or 15
Infusion Duration (hours)	4	2	1	1	1
Premedication					
Methylprednisolone (mg)	100	100	0	0	0
Famotidine (mg)	20	20	20	20	0
Cetirizine (mg)	10	10	10	10	0
Acetaminophen (mg)	650	650	650	650	650

Note that acetaminophen should NOT be discontinued.

5.3.5.2 Clinical Protocol

The schedule of assessment should be followed with regards to visits, labs, and any other required assessments even if TRC105 dosing is held.

6.1.8. Management of TRC105 Infusion Reactions

If a patient experiences a grade 2 or higher adverse reaction during infusion, the infusion should be interrupted and the patient treated accordingly. Antipyretic, antihistamine, antiemetic, anti-inflammatory, or other symptomatic medications including epinephrine may be administered as indicated. For grade 2 and certain grade 3 infusion reactions, the infusion may be restarted at half of the previous rate if and when the infusion reaction has resolved, and then increased per patient tolerance to a maximum of 25 mg/min. For grade 4 infusion reactions, the infusion should not be restarted and the patient should discontinue TRC105 treatment. Infusion reactions will be recorded as AEs in the case report form. Interventions should be documented as concomitant medications or concomitant treatments as appropriate.

Table 13: Management of TRC105 Infusion Reactions

Infusion Reaction Severity	Recommended Management
Grade 1 (mild)	
 1. No intervention 2. Continue infusion unless symptoms worsen
Grade 2 (moderate)	
 1. Interrupt infusion 2. Treat with symptomatic medications^a 3. Resume infusion at half the previous rate when infusion-related symptoms improve to grade 1 or less.
Grade 3 (severe)	
 1. Interrupt infusion 2. Treat with symptomatic medications^a 3. Monitor patient until infusion-related symptoms resolve, including hospitalization if necessary 4. Discontinue TRC105 treatment unless other factors that contributed to the infusion reaction are identified and corrected
Grade 4 (life-threatening)	
 1. Discontinue infusion 2. Treat with symptomatic medications^a 3. Hospitalize patient 4. Discontinue TRC105 treatment

^aSymptomatic medications may include but are not limited to diphenhydramine 50 mg i.v. and/or hydrocortisone 100 mg i.v. (for fever, rash, hypoxia, or other hypersensitivity reactions), meperidine 50-100 mg i.v. (for shaking chills/rigors), oxygen by mask or nasal cannula (for hypoxia), epinephrine 0.5 mg i.m. (for hypotension or bronchospasm), albuterol inhaler or nebulizer (for bronchospasm), i.v. fluids (for hypotension), and ondansetron 0.15 mg/kg i.v. (for nausea).

6.1.9. TRC105 Study Drug Accountability

The Investigator must maintain an accurate accounting of TRC105 supplied by TRACON. During the study, the following information must be recorded:

5.3.5.2 Clinical Protocol

- Date of receipt, quantity and lot number of the TRC105 study drug received from TRACON
- ID number of the patient to whom the product is dispensed
- The date(s) and quantity of the product dispensed
- Dates and quantity of product returned, lost or accidentally or deliberately destroyed

Investigational Drug Accountability Logs should be maintained by the site and must be readily available for inspection.

6.1.10. TRC105 Study Drug Handling and Disposal

TRC105 must be stored upright between 2 °C and 8 °C (36 °F to 46 °F) and protected from light. The Investigator should not return clinical study materials to TRACON unless specifically instructed to do so by TRACON. Used vials do not need to be maintained. All expired vials of TRC105 should be retained until destruction is authorized by a TRACON representative. The Site Pharmacist will be responsible for documenting the destruction (according to institutional requirements) of used or expired vials.

6.2. Description of Pazopanib

See pazopanib package insert [67].

6.2.1. Composition of Pazopanib

See pazopanib package insert [67].

6.2.2. Pazopanib Dose Level

Each patient, except for patients in the angiosarcoma cohort, will be dosed with 800 mg of pazopanib on cycle 1 day 1 and daily thereafter, in the absence of toxicity, once daily without food (at least 1 hour before or 2 hours after a meal) for each day of a 28 day cycle [67]. Note that in phase 1b dose levels 1, 2 and expanded cohort 1 only, cycle 1 will be 14 to 28 days in duration during which pazopanib will be dosed alone. Pazopanib dose reductions are allowed based on individual patient tolerability, including during the initial 2 to 4 week period of the phase 1b when pazopanib is dosed in the absence of TRC105.

Patients in the angiosarcoma cohort 1 will start pazopanib dosing at the time of disease progression on TRC105 single-agent. The starting pazopanib dose will be 800 mg daily in accordance with the package insert. Pazopanib dose reductions are allowed based on individual patient tolerability.

6.2.3. Pazopanib Packaging and Labeling

See pazopanib package insert [67].

6.2.4. Pazopanib Storage Handling and Disposal

See pazopanib package insert [67].

5.3.5.2 Clinical Protocol

6.2.5. Pazopanib Dosing

The recommended starting dose of pazopanib is 800 mg orally once daily without food (at least 1 hour before or 2 hours after a meal). The dose of pazopanib will not exceed 800 mg.

Do not crush tablets due to the potential for increased rate of absorption which may affect systemic exposure.

If a dose is missed, it should not be taken if it is less than 12 hours until the next dose [67].

6.2.6. Pazopanib Dose Modification

Dose increase or reduction is recommended based on individual safety and tolerability. Decrease or increase should be in 200 mg steps based on individual tolerability. The dose of pazopanib will not exceed 800 mg. If a dose is missed, it should not be taken if it is less than 12 hours until the next dose. Patients who cannot tolerate pazopanib or TRC105 therapy and who demonstrate a response of complete response (CR), partial response (PR) or stable disease (SD) with the combination and are thought to benefit from continued single agent therapy may continue on study on TRC105 or pazopanib alone per Section 5.3 of the protocol.

Hepatic Impairment: No dose adjustment is required in patients with mild hepatic impairment. In patients with moderate hepatic impairment, alternatives to pazopanib should be considered. If pazopanib is used in patients with moderate hepatic impairment, the dose should be reduced to 200 mg per day. Pazopanib is not recommended in patients with severe hepatic impairment.

- Patients with isolated ALT elevations between 3 X ULN and 8 X ULN may be continued on pazopanib with weekly monitoring of liver function until ALT return to Grade 1 or baseline.
- Patients with isolated ALT elevations of >8 X ULN should have pazopanib interrupted until they return to Grade 1 or baseline. If the potential benefit for reinitiating treatment with pazopanib is considered to outweigh the risk for hepatotoxicity, then reintroduce pazopanib at a reduced dose of no more than 400 mg once daily and measure serum liver tests weekly for 8 weeks. Following reintroduction of pazopanib, if ALT elevations >3 X ULN recur, then pazopanib should be permanently discontinued.
- If ALT elevations >3 X ULN occur concurrently with bilirubin elevations >2 X ULN, pazopanib should be permanently discontinued. Patients should be monitored until resolution. pazopanib is a UGT1A1 inhibitor. Mild, indirect (unconjugated) hyperbilirubinemia may occur in patients with Gilbert's syndrome. Patients with only a mild indirect hyperbilirubinemia, known Gilbert's syndrome, and elevation in ALT >3 X ULN should be managed as per the recommendations outlined for isolated ALT elevations.

Blood pressure should be monitored and managed promptly using a combination of anti-hypertensive therapy and dose modification of pazopanib (interruption and re-initiation at a reduced dose based on clinical judgment).

Increased blood pressure should be treated promptly with standard anti-hypertensive therapy and dose reduction or interruption of pazopanib as clinically warranted. pazopanib should be discontinued if there is evidence of hypertensive crisis or if hypertension is severe and persistent

5.3.5.2 Clinical Protocol

despite anti-hypertensive therapy and dose reduction. Approximately 1% of patients required permanent discontinuation of pazopanib because of hypertension [67].

Interrupt pazopanib and dose reduce for 24-hour urine protein ≥ 3 grams; discontinue pazopanib for repeat episodes despite dose reductions.

Institute appropriate anti-infective therapy promptly and consider interruption or discontinuation of pazopanib for serious infections.

Interruption of therapy with pazopanib is recommended in patients undergoing surgical procedures [67]. TRC105 and pazopanib should be held for two weeks prior and for two weeks following surgical procedures. For **minor procedures** (e.g., port placement), TRC105 (and pazopanib) should be held for at least 1 week prior and for at least 1 week after (or until adequate healing).

6.2.7. Pazopanib Drug Accountability

Patients will be asked to return any unused tablets from the previous cycle for proper drug accountability and destruction according to institution guidelines. A new prescription will be dispensed for the following cycle.

6.3. Concomitant Medications

No other approved or investigational anticancer treatment will be permitted during the study period. No other investigational drug may be used during treatment on this protocol, and concurrent participation in another clinical trial is not allowed.

Patients who receive NSAIDs on study should also receive peptic ulcer disease (PUD) prophylaxis with an H2 or proton pump blocker.

Narcotic analgesics, nonsteroidal anti-inflammatory drugs, and triptans (e.g. sumatriptan) may be offered as needed for relief of pain or headaches. Antihistamines and decongestants may be offered for the treatment of sinus congestion.

Packed red blood cell, colony stimulating factors, and platelet transfusions should be administered as clinically indicated.

CYP3A4 Inhibitors: Avoid use of strong inhibitors ([Table 14](#)); co-administration of pazopanib with strong inhibitors of CYP3A4 increases pazopanib concentrations. Patients may not have received a strong CYP3A4 inhibitor within 7 days prior to cycle 1 day 1. If co-administration is warranted, reduce the dose of pazopanib to 400 mg.

CYP3A4 Inducers: Consider an alternate concomitant medication with no or minimal enzyme induction potential; CYP3A4 inducers may decrease plasma pazopanib concentrations. Pazopanib should not be used if chronic use of strong CYP3A4 inducers cannot be avoided. Patients may not have received a strong CYP3A4 inducer within 12 days prior to cycle 1 day 1.

CYP Substrates: Concomitant use of pazopanib with agents with narrow therapeutic windows that are metabolized by CYP3A4, CYP2D6, or CYP2C8 is not recommended.

5.3.5.2 Clinical Protocol

Concomitant use of pazopanib and simvastatin increases the risk of ALT elevations and should be undertaken with caution and close monitoring.

Table 14: Strong CYP3A4 Inducers and Inhibitors^a

Inducers:	*^aInhibitors:	
dexamethasone	Boceprevir	Conivaptan
phenytoin	Indinavir	Itraconazole
carbamazepine	Nelfinavir	Ketoconazole
rifampin	Lopinavir/ritonavir	Mibefradil
rifabutin	Saquinavir	Nefazodone
rifapentin	Telaprevir	Posaconazole
phenobarbital	Ritonavir	Voriconazole
St. John's Wort	Clarithromycin	Telithromycin

^a Because the lists of these agents are constantly changing, it is important to regularly consult a comprehensive list such as the one located at <http://medicine.iupui.edu/clinpharm/ddis/>.

